CLINICAL PROTOCOL

Ultrasound-guided Placement of Peripheral Intravenous Lines in the Internal Jugular Vein

NCT03231345

Last updated April 1, 2017

INTRODUCTION:

Intravenous (IV) access in the emergency department (ED) patient is essential for medication delivery, IV fluid resuscitation, rapid serum laboratory diagnostics, and administration of IV contrast for CT scans. Some patients, such as those with obesity, IV drug abuse, chronic illnesses, or vascular pathology may have difficult IV access. These patients are problematic for the busy ED nurse and physician as this can lead to a time consuming process, which slows efficiency and patient care.

Previously, patients with difficult IV access often ended up getting central venous catheterization, a procedure that can result in a number of serious complications (1). More recently, ultrasound guidance has been touted as an effective means to achieve peripheral IV access on these patients (2). In one study (2), there was a 73% first attempt cannulation rate, which seems respectable, but not excellent. Additionally, 8% of the successful IVs failed within one hour (2). Another study compared ultrasonographically guided peripheral IVs to non-ultrasonographically guided IVs, and it found that using ultrasound did not decrease the amount of time or the number of attempts it took to successfully place a peripheral IV (3).

It seems that we still have room to improve our ability to obtain difficult IV access, and a relatively new technique may be the answer. Ultrasound guided IVs are typically attempted in the upper extremities, targeting the brachial or basilic veins, but a recently described technique --- the "peripheral IJ" --- involves placement of a peripheral IV catheter in the internal jugular vein (4,5).

The peripheral IJ is gaining popularity in our ED as a solution to the difficult vascular access patient. In our clinical experience, it is a quick and easy procedure that is also safe, tolerated well by patients, and requires fewer resources. Several small studies have concluded that this is a fast and safe procedure and a feasible alternative to central access in the difficult vascular access patient (4-7). These studies mention the theoretical risks as being similar to central venous access such as carotid artery puncture, hematoma, pneumothorax, and line infection, however none of these have actually been reported (4-7).

We feel it is important to continue to contribute to the knowledge about the safety, speed, and feasibility of ultrasound-guided internal jugular vein peripheral cannulation. We

propose a prospective evaluation of peripheral IJ placement on a convenience sample of emergency department patients who require IV access and have difficult IV access. Therefore, we seek primarily to determine the average number of attempts to cannulation for ultrasound-guided peripheral IJ placement. Secondarily, we wish to determine: 1) the prevalence of potential complications related to this procedure 2) the average time it takes the emergency physician to complete the procedure 3) the patient's satisfaction with the procedure. This data will be compared to the existing literature on ultrasound-guided peripheral IV placement using other techniques.

METHODS:

This will be a prospective study at a single, urban, academic emergency department evaluating the placement of peripheral IJs on a convenience sample of patients with difficult IV access ED patients who require IV access for medical management.

Inclusion criteria:

- * At least two unsuccessful attempts at peripheral IV access by ED nursing staff.
- * Age >18.

Exclusion criteria:

- * Critically ill patients with clinical indications for emergent central venous access.
- * Overlying skin infection.
- * External jugular vein easily visible for cannulation.
- * Patients in law enforcement custody.
- * Patients who are pregnant.
- * Patients who lack decision-making capacity

ED residents and attending physicians will perform ultrasound-guided cannulation of the IJ using aseptic technique. A biopatch and sterile dressing will be placed. This is similar to the technique used to place traditional central venous catheters. Standard catheter over needle method will be used, and the catheter will be secured in typical fashion as for a standard IV start.

A data collection form will be available for completion by a trained observer (who will observe the physician placing the IV). Data collection will include location, number of attempts, time to successful completion, post-procedure portable chest x-ray results, immediate complications, catheter type used, time to discontinuation of catheter, reason for catheter removal, delayed complications, and patient demographics.

For patients who end up getting admitted, data regarding discontinuation of the catheter, reason for removal, and delayed complications will be obtained from the inpatient nursing charts.

Although many of our ED physicians already use the peripheral IJ technique, all residents and attending physicians involved in this study will be required to attend a mandatory

training session about the placement of peripheral IJs to ensure adequate baseline knowledge of the technique.

The largest study to evaluate the placement of peripheral IJs had 33 patients (4). We hope to enroll 50 patients. Each patient will sign a written consent form.

In order to protect the privacy of the research subjects and to maintain the confidentiality of data, all data will be handled only by research assistants or investigators and will be stored only in secure cabinets in locked research offices.

REFERENCES:

- (4) Teismann, N. A., Knight, R. S., Rehrer, M., Shah, S., Nagdev, A., & Stone, M. (2013). The Ultrasound-guided "Peripheral IJ": Internal Jugular Vein Catheterization using a Standard Intravenous Catheter. The Journal of Emergency Medicine, 44(1), 150-154.

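### Convenience sampling of individual patients, for a technique already used off study and with no count of those missed, can bias the single-arm averages in a way the data cannot reveal

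*Protocol*

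**What the plan says.** The sampling method is stated twice. The last paragraph of the Introduction proposes a "prospective evaluation of peripheral IJ placement on a convenience sample of emergency department patients", and the first paragraph of the Methods repeats it as "a convenience sample of patients with difficult IV access ED patients who require IV access for medical management". In both places the unit of convenience is the patient. No enrolment shifts or periods are fixed.

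The technique is already practised at the site. The Introduction says "The peripheral IJ is gaining popularity in our ED as a solution to the difficult vascular access patient", and the training paragraph of the Methods says that "many of our ED physicians already use the peripheral IJ technique". The Introduction also records the investigators' prior view: "In our clinical experience, it is a quick and easy procedure that is also safe".

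On conduct, the Methods state that "ED residents and attending physicians will perform ultrasound-guided cannulation of the IJ using aseptic technique" and that "A data collection form will be available for completion by a trained observer", who watches the placement. Each patient gives written consent, and the hoped-for enrolment is 50.

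The primary aim is the average number of attempts to cannulation. Complications, procedure time and satisfaction are secondary. All are to be set against published results for other ultrasound-guided techniques. There is no concurrent control.

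The protocol does not state:
- who selects or approaches patients;
- whether consent or registration must precede the first skin puncture;
- any count of eligible patients who were not enrolled;
- any count of peripheral IJ lines placed outside the study.

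**The concern.** The study's results are absolute figures from one group. In a controlled comparison, selection acting equally on both arms largely cancels. Here it enters the primary estimate directly.

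Because the technique is available outside the study, an eligible patient whose neck looks difficult could receive the line off study, or never be approached, with no deviation from the protocol. The eligibility criteria do not close this route, since none requires that everyone who meets them be approached. The observer protects the recording of attempts in an observed case but has no bearing on which cases are observed. With no registration point before the first puncture, the protocol also does not exclude enrolment decided after a placement has begun.

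A confidence interval will not reflect any of this, and a larger sample would not shrink it. A statistical analysis plan cannot repair it either, because a denominator that was never recorded cannot be recovered at analysis.

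**Working it through.** The protocol gives no figure for selection, so there is nothing of its own to reproduce. The target of 50 comes with no power or precision input and is placed beside an earlier study of 33 patients. What follows only illustrates how large the effect could be.

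**Inputs from the protocol:** n = 50; primary outcome mean attempts; 73% first-attempt success quoted in the Introduction from a published study of other veins.

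**Assumed inputs:** 40% of eligible patients are hard; first-attempt success is 60% in hard and 85% in easy cases; easy cases are k times as likely to be enrolled as hard ones. Attempts are independent with constant success probability and continue until success (geometric model).

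**Formulas**
- Hard share among enrolled: s = 0.4 / (0.4 + 0.6k)
- Mean attempts: (1 − s)/0.85 + s/0.60
- First-attempt rate: 0.85(1 − s) + 0.60s

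| k | s | First-attempt rate | Mean attempts | Shift in mean |
|---|---|---|---|---|
| 1 (no selection) | 0.400 | 75.0% | 1.37 | – |
| 2 | 0.250 | 78.8% | 1.30 | −0.07 |
| 4 | 0.143 | 81.4% | 1.25 | −0.13 |
| 0.5 (hard cases favoured) | 0.571 | 70.7% | 1.46 | +0.08 |

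**Sampling error of the mean at k = 1**
- The mean square of a geometric variable is (2 − p)/p². The mixture gives 0.6 × 1.15/0.7225 + 0.4 × 1.40/0.36 = 0.955 + 1.556 = 2.511.
- Variance = 2.511 − 1.3725² = 0.627, so the SD is 0.79.
- Standard error = 0.79/√50 = 0.11, and the 95% half-width is about 0.22.

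The k = 2 shift of 0.07 is about two thirds of one standard error. The k = 4 shift of 0.13 is about one. Neither reaches the 95% half-width.

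**Second set of assumptions, tied to the 73% in the protocol.** Take success of 85% and 50%. The hard share that gives 73% overall is (0.85 − 0.73)/(0.85 − 0.50) = 0.34.
- If hard cases are half as likely to be enrolled, s falls to 0.21 and mean attempts fall from 1.46 to 1.35, a shift of 0.11. With hard shares of 0.20 and 0.50 the falls are 1.34 to 1.27 and 1.59 to 1.45. The 95% half-width, from a simple geometric model at 73%, is about 0.20.
- If hard cases are 1.5 times as likely to be enrolled, mean attempts rise to 1.54.
- With assumed complication rates of 1% (easy) and 6% (hard), halving the inclusion of hard cases lowers the expected rate from 2.7% to 2.0%. The chance of seeing no complication in 50 patients, (1 − rate)^50, rises from 25% to 36%.

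Both sets agree: moderate selection moves the primary estimate by an appreciable part of its sampling error, and the sign depends on who is over-enrolled.

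**The case against.** The strongest reply is that convenience sampling is openly declared, in two places, for a small single-site study that nowhere claims a representative sample. That is true, and the point corrects no misstatement. But declaring the method does not make its effect measurable, and the comparison with the literature is a stated purpose of the study.

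Several stronger readings are tempting, and the protocol does not support them.

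- *Operators choose their own cases.* The protocol never says who selects patients. Since an observer watches the placement, inclusion may follow observer availability, which need not track difficulty.
- *The results will look too good.* The investigators' favourable view makes this plausible. But the technique is also presented as an answer to difficult access, so physicians could reserve it for the hardest patients, which would raise mean attempts.
- *The bias matches or exceeds sampling error.* On the primary scale, with 60% and 85% success, it does not at k = 2 and is only about one standard error at k = 4. Every input is assumed.
- *Forms are optional for enrolled patients.* The wording about the form being available is loose, but the next sentence lists what data collection will include. The gap is that no rule ties a form to every registered patient.
- *The literature comparison is biased by the same amount.* That depends on how the cited studies sampled their patients, which the protocol does not give.
- *The remedy needs no extra staff.* The protocol describes an observer at the procedure, not observer shifts. Screening and logging are additional work.

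It also stands that only trained physicians take part, that patients may refuse, and that choice of access route remains clinical. Consecutive approach therefore reduces selection and makes it visible but does not remove it.

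**Conclusion.** The point holds as a design weakness worth a cheap correction. The protocol can be followed exactly and still give selected averages, with no denominator by which a reader could judge them. The conclusion that bias is possible and undetectable rests on the text alone: patient-level convenience sampling, off-study use of the technique, a single arm, and no registration point or log.

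The size rests on assumptions. In the first illustration the primary estimate shifts by 0.07 attempts at twofold and 0.13 at fourfold preference for easy cases, against a standard error of about 0.11, and the shift reverses if hard cases are preferred. The geometric model behind these figures is itself an assumption. The documents show neither that selection will occur nor its direction.

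**What to change.** 1. In both places (last paragraph of the Introduction, first paragraph of the Methods), replace the convenience-sample wording with a rule such as: during periods when a trained observer is available, all eligible patients in whom a participating physician plans a peripheral IJ will be approached consecutively. The clinical choice of access route stays as it is.
2. Register each consented patient before the first skin puncture.
3. Where the Methods now say "A data collection form will be available for completion by a trained observer", state that the observer completes the form for every registered patient.
4. Keep all registered patients in the analysis, including failed placements.
5. Keep a one-line log, for the same periods, of eligible patients not enrolled (with the reason) and of known peripheral IJs placed off study. Report the enrolled fraction with the results.

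The cost is a wording amendment and modest screening and logging effort. If observers are called case by case, so that fixed periods cannot be defined, the registration rule, the log and the reported fraction still apply.

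### Does it matter that the protocol's data list names no operator, grade or prior experience behind the average attempts and time?

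*Protocol*

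**What the plan says.** The last paragraph of the Introduction sets the primary aim: "we seek primarily to determine the average number of attempts to cannulation for ultrasound-guided peripheral IJ placement". One of the three secondary aims is "the average time it takes the emergency physician to complete the procedure"; the other two are complications and patient satisfaction. The results are to be set against published work on other ultrasound-guided techniques.

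Methods states who does the procedure: "ED residents and attending physicians will perform ultrasound-guided cannulation of the IJ using aseptic technique". The training paragraph starts "Although many of our ED physicians already use the peripheral IJ technique, all residents and attending physicians involved in this study" and goes on to require a training session for all of them, so that each has sufficient basic knowledge of the technique.

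On data capture, Methods says "A data collection form will be available for completion by a trained observer (who will observe the physician placing the IV"). The list that follows opens with "Data collection will include location, number of attempts, time to successful completion, post-procedure portable chest x-ray results, immediate complications, catheter type used" and closes with "time to discontinuation of catheter, reason for catheter removal, delayed complications, and patient demographics". For admitted patients, "data regarding discontinuation of the catheter, reason for removal, and delayed complications will be obtained from the inpatient nursing charts". That sentence gives a source for three items already listed and adds no new ones.

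**The concern.** Both the primary outcome and the time outcome measure a physician's performance. Two grades of physician place lines, and many of them, not all, already use the technique. If neither the operator nor the grade is recorded, a reader cannot tell whether the average reflects mostly residents or mostly attendings. Nor can an analyst see whether a few physicians placed most of the lines, in which case the 50 placements would carry less information than 50 independent ones. A later analysis plan cannot recover a variable that was never written down, so it is reasonable to look for it in the protocol. At stake would be the description of the operators, the generalisability of the averages and the honesty of any confidence interval.

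**Working it through.** **1. Item check.** The ten listed items are: location, attempts, time to completion, chest x-ray, immediate complications, catheter type, time to discontinuation, reason for removal, delayed complications and patient demographics. Items giving operator, grade or experience: 0 of 10. The observation is correct as far as the list goes.

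**2. Is the list meant to be complete?** Set the aims beside the items.

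| Aim (Introduction) | Listed item (Methods) |
|---|---|
| Average attempts (primary) | number of attempts |
| Complications | chest x-ray, immediate and delayed complications |
| Average procedure time | time to completion |
| Patient satisfaction | none |

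One stated aim has no listed item, and the list is introduced as things that data collection will include. Absence from the list is therefore weak evidence that something will not be recorded. The form itself is not shown.

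**3. Does any aim need an operator field?** No result by operator, grade or experience is promised. With p the share of placements by residents, the pooled mean is p × (resident mean) + (1 − p) × (attending mean). It is the sum of attempts divided by the number of placements, and it is the correct average for the mix that occurred, whether or not p is written down. Not knowing p limits description; it does not bias the figure.

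**4. How far could the mix move the average?** The document gives no difference d between grades, so d is assumed. Comparing two hypothetical studies with 20% and 80% residents, shift = d × (0.80 − 0.20):
- d = 0: 0
- d = 0.25: 0.15 attempts
- d = 0.5: 0.30 attempts
- d = 1.0: 0.60 attempts

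This is a difference between two imagined studies. It is not an error in this one.

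**5. Clustering.** The document gives neither the number of operators nor an intra-operator correlation (ICC), so both are assumed. For n = 50 placements with m lines per operator, the design effect is DE = 1 + (Σm²/n − 1) × ICC, and the standard error is multiplied by √DE.

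| Operators | Σm²/n | DE at ICC 0 / 0.05 / 0.10 / 0.20 | Increase in SE |
|---|---|---|---|
| 50 placing 1 each | 1 | 1.00 / 1.00 / 1.00 / 1.00 | 0% throughout |
| 25 placing 2 each | 2 | 1.00 / 1.05 / 1.10 / 1.20 | 0 / 2.5 / 4.9 / 9.5% |
| 5 placing 6, 20 placing 1 | (180 + 20)/50 = 4 | 1.00 / 1.15 / 1.30 / 1.60 | 0 / 7.2 / 14.0 / 26.5% |
| 10 placing 5 each | 5 | 1.00 / 1.20 / 1.40 / 1.80 | 0 / 9.5 / 18.3 / 34.2% |

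The increase matters only if an interval is reported, operators repeat and the ICC is above zero. The protocol states none of these.

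**6. What would the fields buy?** The 95% half-width for a resident–attending difference, in SD units and treating placements as independent, is t(0.975, 48) × √(1/n₁ + 1/n₂), with t = 2.011:
- 25/25 split: 2.011 × 0.283 = 0.57 SD
- 40/10 split: 2.011 × 0.354 = 0.71 SD

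A comparison by grade would be descriptive only. In the comparison with published series, technique, operators and setting all differ together, and these fields would not separate them.

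**The case for a change.** The strongest argument for the concern is that the choice of variables is a protocol matter, not one to leave to the analysis plan, and that this protocol sets out its list explicitly. The authors themselves treat operator preparation as important, since they require training. A training session sets a minimum of knowledge; it does not record who placed each line. The remedy would be cheap: a few short fields on a form filled in by someone already watching the physician.

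Much of this stands. The items are not listed, training does not replace recording them, and a missing operator code could not be restored by analysis. The fields would help a reader describe the operators and would allow for clustering if it arose.

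What does not stand is the step from not listed to wrongly planned. The list does not claim to be exhaustive, the unseen form may already carry the fields, and every stated aim concerning attempts and time can be met without them. The missing satisfaction item could be read as a sign that the list should be completed, but that is a separate matter and says nothing about operators. The argument that the fields are useful and cheap supports a suggestion; it does not show a fault.

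**Conclusion.** The concern does not hold as an error in the plan. The protocol contains no wrong statement or contradiction on this point, and its averages of attempts and time remain valid summaries for the operators it discloses. The effect of having no operator field cannot be sized from the document and may be nil. The figures of 0 to 0.60 attempts between hypothetical mixes and 0% to 34% on a standard error rest wholly on assumed grade differences, operator numbers and correlations, and each range includes zero. The conclusion rests on two readings: that the data list is illustrative, which its wording and the unlisted satisfaction item support, and that no result by operator or grade is intended, since none is stated. If the investigators later wished to report by grade, or to attach an interval to results from a few repeating operators, an operator code would be needed.

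### For admitted patients, delayed complications are taken from nursing charts alone, so the delayed part of the complication objective is likely to be under-counted

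*Protocol*

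**What the plan says.** The first of the three secondary objectives, at the end of the Introduction, is "the prevalence of potential complications related to this procedure". Earlier in the Introduction the protocol names the theoretical risks and describes the published experience: "carotid artery puncture, hematoma, pneumothorax, and line infection, however none of these have actually been reported".

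The Methods section sets up two routes for collecting complications.

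- **At placement.** "A data collection form will be available for completion by a trained observer", and the items collected include "post-procedure portable chest x-ray results, immediate complications, catheter type used". Delayed complications and the reason for catheter removal are also on the list of items.
- **After admission.** For patients who are admitted, "reason for removal, and delayed complications will be obtained from the inpatient nursing charts". Catheter discontinuation comes from the same charts.

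No culture result, imaging report, physician note or discharge diagnosis is named as a source of delayed complications in admitted patients. The protocol defines neither a delayed complication nor a line infection. On sample size it says "We hope to enroll 50 patients". On use of the results it says "This data will be compared to the existing literature on ultrasound-guided peripheral IV placement using other techniques".

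**The concern.** The issue is the type of record, not who is followed or for how long. A nursing chart is a natural place to find when and why a catheter came out. It is not ordinarily where a line infection is diagnosed or where a late pneumothorax or neck hematoma is confirmed. Those rest on cultures, imaging and a physician's assessment. If a diagnosis made elsewhere in the inpatient record is not carried into the nursing chart, the study as written has no other named place to find it.

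The likely error runs in one direction that matters here. The background is that none of the named complications has been reported, and the results will be set beside published work. An insensitive source makes a result of no delayed events more likely, and that result would look like confirmation of the background even if events had occurred. This is also a stated choice of data source, not a detail left open for an analysis plan to supply.

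**Working it through.** **Figures in the protocol.** The only relevant number is the planned enrolment of 50 (Methods). It is set beside an earlier series of 33 patients, with no complication rate, precision or power behind it, so there is no stated calculation to reproduce.

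**Which named risks depend on the nursing chart in admitted patients.**

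| Risk named in the Introduction | Observer form or post-procedure x-ray | Named source if it appears later in an admitted patient |
|---|---|---|
| Carotid puncture | Yes, at placement | Nursing chart, for any late consequence |
| Hematoma | Yes, if evident at placement | Nursing chart |
| Pneumothorax | Yes, if visible on that film | Nursing chart |
| Line infection | No, it develops after placement | Nursing chart |

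Line infection is the one named risk with no route at placement.

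**Illustration of size.** Let *n* be the number of patients, *a* the share admitted, *p* the true rate of delayed complications, and *s* the probability that the nursing chart records a true event. Only *n* = 50 is in the protocol; *a*, *p* and *s* are assumptions. False entries are taken as absent.

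1. Exact two-sided 95% upper limit after no recorded events, all 50 admitted: 1 − 0.025^(1/50) = 7.1%. This follows from sample size alone, whatever the record.
2. The recorded rate is *p* × *s*, so the limit on the true rate is 7.1% / *s*:
   - *s* = 0.8: 7.1 / 0.8 = 8.9%
   - *s* = 0.5: 7.1 / 0.5 = 14.2%
   - *s* = 0.3: 7.1 / 0.3 = 23.7%
3. Chance of recording no event, (1 − *p* × *s*)^50, at an assumed *p* of 5%:
   - *s* = 1: 0.95^50 = 7.7%
   - *s* = 0.5: 0.975^50 = 28.2%
4. Expected events at an assumed *p* of 6% and *s* = 0.5:
   - All admitted: 50 × 0.06 = 3 true events, 1.5 recorded and 1.5 missed.
   - Half admitted (assumed): 25 × 0.06 = 1.5 true events, 0.75 recorded and 0.75 missed.
5. Limit with 25 admitted and no recorded event among them: 1 − 0.025^(1/25) = 13.7%, and 13.7 / 0.5 = 27.4% at *s* = 0.5.

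Steps 4 and 5 show why the share admitted matters. With fewer admissions, fewer events can be missed, but less can be said about the true rate in those patients.

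**The case against.** The strongest reply is that nothing in the protocol says what these nursing charts contain. A nurse may record a culture result or a physician's diagnosis, and reason for removal is a separate item, so a catheter taken out for suspected infection has a second way of being noticed. That stands. A reader might infer that nursing charts cannot show a line infection and that bias has been demonstrated. The documents do not support this; under-counting is a likely risk of unknown size. Reason for removal does not close the gap, because it comes from the same chart and would not show an infection recognised after the catheter was out or removed for another stated reason.

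A second reply is that most of the named risks are covered at placement by the observer and the x-ray. This also stands, and it limits the scope. A reader might conclude that the whole complication prevalence is biased toward zero. Only its delayed part, and only in admitted patients, depends on this source.

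A third reply is that the 14% figure merely rescales 7.1% by an assumed sensitivity and treats everyone as admitted. That is correct, and the figure should not be read as an estimate of the bias.

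Finally, reading more records without a definition could over-count. A positive blood culture from the presenting illness is not a complication of the catheter, and the objective concerns complications related to the procedure. The absence of a definition also means that a nursing chart could yield some false positives. Both points shape the fix but do not remove the need for it.

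**Conclusion.** The point holds in a limited form. For admitted patients the protocol names a single record type for delayed complications, and that record is not where line infection, late pneumothorax or late hematoma is ordinarily confirmed. The delayed part of the first secondary objective is therefore likely to be too low in these patients. No figure in the protocol is wrong, and the primary objective, the number of attempts, is not affected.

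The size cannot be derived from the protocol, which gives neither the sensitivity of the charts nor the share of patients admitted. The illustrative widening of the upper limit, from 7.1% to about 14% (9% to 24%), rests on three assumptions: all 50 patients admitted, no false entries, and a sensitivity of 50% (80% to 30%). It shows how weak the reassurance from an empty column could be. It does not show that events will be missed at that rate. The judgement about where these diagnoses are confirmed is general clinical practice, not a statement in the protocol.

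**What to change.** Split the Methods sentence on admitted patients in two.

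- Nursing charts continue to supply the date of and reason for catheter removal.
- Delayed complications are abstracted from the full inpatient record: nursing notes, culture results, chest and neck imaging reports, and physician and discharge diagnoses. This is done against a pre-set list, with a short definition of each event and a rule for attributing it to the catheter, so that events arising from the presenting illness are not counted.

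The report should state how many patients were admitted and give delayed complications with that denominator, separately from immediate ones.

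The cost is a few more minutes of chart review per admitted patient, for at most 50 patients, plus the work of writing the list and definitions beforehand. The reported complication rate may be less favourable. Enrolment, the procedure and patient care do not change.
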